7.2.2 Patient Selection

7.2.2.1 Inclusion Criteria

Four cohorts will be created based on healthcare setting and type of steroid use. Their eligibility criteria being described below (using Covid-19 catch-all definition Section 7.3.1):

Ambulatory prevalent user

- Have at least 365 days of continuous observation time prior to cohort entry
- Have a glucocorticoid (oral or parenteral) exposure in the 120 days prior to diagnosis date (unrelated to COVID-19 diagnosis)
- Have a positive PCR test for SARS-CoV-2 (labCOVID-19) or a confirmed COVID-19 diagnosis (diagCOVID-19)
- Have no hospitalizations in the 30 days prior to or on index

Ambulatory naive user

- Have at least 365 days of continuous observation time prior to cohort entry
- Have no glucocorticoid (oral or parenteral) exposure in the 120 days prior to index (unrelated to COVID-19 diagnosis)
- Have a positive PCR test for SARS-CoV-2 (labCOVID-19) or a confirmed COVID-19 diagnosis (diagCOVID-19)
- Have no hospitalizations in the 30 days prior to or on index

Hospitalized prevalent user

- Have a glucocorticoid (oral or parenteral) exposure in the 120 days prior to index (unrelated to COVID-19 diagnosis)
- Have a positive PCR test for SARS-CoV-2 (labCOVID-19) or a confirmed COVID-19 diagnosis (diagCOVID-19) (index date)
- Are hospitalized 30 days prior or after diagnosis index date
- Have no intensive services in the 30 days prior to or on index

Hospitalized naïve user

- Have no prior exposures to glucocorticoids in the 120 days prior to index
- Have a positive PCR test for SARS-CoV-2 (labCOVID-19) or a confirmed COVID-19 diagnosis (diagCOVID-19)
- Are hospitalized 30 days prior or after diagnosis index date
- Have no intensive services in the 30 days prior to or on index

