7.3.2.1 Glucocorticoids

Glucocorticoids used in COVID-19 indication

The primary treatment group of interest is based on exposure to systemic glucocorticoids. The following drugs will be considered as being used for COVID-19 diagnosis:

- Dexamethasone (H02AB02)
- Prednisone (H02AB07)
- Prednisolone (H02AB06)
- Methylprednisolone (H02AB04)
- Hydrocortisone (H02AB09)

Only glucocorticoids which were investigated in clinical trials (13,21) or are recommended by clinical guidelines are included (22–24) to avoid misclassification of steroids used for other conditions. As indication is not captured in the available databases, a glucocorticoid treatment will be considered to have been initiated for COVID-19 treatment if:

For incident users

- The glucocorticoid treatment was initiated between 2 before and 30 days after COVID-19 diagnosis date (21)
- It is one of the five glucocorticoids recommended for COVID-19 as above

For prevalent users

- The glucocorticoid treatment was initiated between 2 before and 30 days after COVID-19 diagnosis date
- It is one of the five glucocorticoids recommended for COVID-19 as above
- The glucocorticoid started after COVID-19 diagnosis differs from the chronically used glucocorticoids OR there is a change in dose or schedule of administration compared to the prevalent use, occurred after COVID-19 diagnosis.

Glucocorticoids for pre-existing conditions

For the prevalent users, any steroid in the ATC class H02 glucocorticoids for systemic use will be considered. A patient is defined as a systemic glucocorticoids prevalent user if it has at least one prior exposure to systemic² glucocorticoids in the 120 days prior to diagnosis index date.

For the description of prevalent users of glucocorticoids, categories of use will be created based on proportion of days covered (PDC) during the lookback period. PDC is calculated as the number of days in period covered by prescriptions divided by number of days in the period.

- PDC > 85% as heavy user
- PDC 50-85% as moderate user
- less than 50% PDC as light user

Another categorization of prevalent glucocorticoids user will be based on how recently in the past the last prescription was observed:

- current use (concomitant on date of COVID-19 diagnosis)
- recent use (between 15-30 days before date of COVID-19 diagnosis)
- remote use (use ended more than 30 days before date of COVID-19 diagnosis)

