7.7.2 Glucocorticoid prescribing patterns (primary objective 1)

Prescribing patterns of systemic glucocorticoids for the treatment of COVID-19 will be summarized by the four cohorts (section 7.2.2) and by subgroups of special interest (section 7.2.4) and the description will include time to initiation of glucocorticoid treatment (from COVID-19 diagnosis), duration of treatment, route of administration, daily dose at start, cumulative dose and duration of

treatment received post COVID-19 diagnosis, see section 7.3.2 for details regarding calculation of exposure parameters .

Frequency of concomitant use of other medications and invasive/non-invasive respiratory support at COVID-19 diagnosis index date and during follow-up will also be presented.

The time to systemic glucocorticoid initiation from COVID-19 diagnosis will be modelled as a time-to-event outcome using the Kaplan-Meier (KM) estimator. The patient follow-up from COVID-19 diagnosis date until systemic glucocorticoid treatment index date will be included in the KM analysis, with start of systemic glucocorticoid therapy being considered a ‘failure’ event. This KM analysis will be stratified by route of systemic glucocorticoid administration (oral vs intravenous). The KM survival function curve (95% CI) and summary statistics of 25th percentile, median, 75th percentile of time to event (in days) will be provided. The survival function within each stratification will be compared using log-rank test.

A time series graph will be used to investigate changes in prescribing patterns over calendar time. Monthly and quarterly incidence steroid incident use will be plotted against time from January 2020 until study end. Key dates (such as Recovery trial) should be highlighted on this graph to allow differentiation between time periods. A formal before /after analysis is not proposed. Results will be stratified per country and per database.

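### The two days before diagnosis on which a COVID-19 glucocorticoid may start lie inside the 120-day look-back, so a first-ever start on day −2 or −1 is classified inconsistently and, in hospital, fits no cohort

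*Protocol*

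**What the plan says.** Five statements in the protocol bear on this point.

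- **Exposure window, 7.3.2.1, incident users:** "The glucocorticoid treatment was initiated between 2 before and 30 days after COVID-19 diagnosis date (21" (the closing number is a citation). Prevalent users get the same window. The drug must also be one of five listed glucocorticoids.
- **Prevalent-user definition, 7.3.2.1:** a patient is prevalent with "at least one prior exposure to systemic² glucocorticoids in the 120 days prior to diagnosis index date". No exception is made for use that belongs to the COVID-19 episode.
- **Extra condition for prevalent users, 7.3.2.1:** "The glucocorticoid started after COVID-19 diagnosis differs from the chronically used glucocorticoids OR there is a change in dose or schedule of administration". The text places that change after diagnosis as well.
- **Hospital cohorts, 7.2.2.1:** the naive cohort must "Have no prior exposures to glucocorticoids in the 120 days prior to index". The prevalent cohort must "Have a glucocorticoid (oral or parenteral) exposure in the 120 days prior to index (unrelated to COVID-19 diagnosis"). Both ambulatory criteria also carry the qualifier about use unrelated to COVID-19. Hospitalized naive is the only one of the four without it.
- **Time to initiation, 7.7.2:** "The patient follow-up from COVID-19 diagnosis date until systemic glucocorticoid treatment index date will be included in the KM analysis".

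Section 7.3.2.1 also states that indication is not captured. Whether a course is unrelated to COVID-19 can therefore be inferred only from timing and drug.

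**The concern.** A start on day −2 or −1 satisfies the timing rule for COVID-19 treatment and, at the same time, is an exposure in the 120 days before diagnosis. The protocol does not say which rule takes precedence, and its sections give different answers.

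User type and time to initiation are both listed variables of the primary objective (6.2). User type also defines the four cohorts, and the treatment index date starts follow-up for secondary objectives 2 and 3. Two programmers could each follow the text faithfully and build different cohorts. In one, patients treated just before diagnosis disappear from the hospital analysis. In the other, they appear as prevalent users without COVID-19 glucocorticoid treatment.

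**Working it through.** No figure in the protocol can be reproduced here, so the check applies the rules literally to one patient. This patient has no steroid history and starts one of the five listed drugs on day d relative to diagnosis, on a stable regimen. In the 7.2.2.1 columns, a start from day −2 to day +30 is taken as COVID-19-related.

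| Start day d | 7.2.2.1, ambulatory | 7.2.2.1, hospital | 7.3.2.1, user type | 7.3.2.1, counts as COVID-19 glucocorticoid |
|---|---|---|---|---|
| −3 | prevalent | prevalent | prevalent | no |
| −2 or −1 | naive | neither cohort | prevalent | no |
| 0, +1, +30 | naive | naive | naive | yes |

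The conflict is confined to days −2 and −1. Four steps explain that row.

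1. **Hospital, 7.2.2.1.** Hospitalized naive fails because any use in the prior 120 days is barred. Hospitalized prevalent fails because the only prior use is COVID-19-related. The patient is in 0 of 2 hospital cohorts.
2. **Ambulatory, 7.2.2.1.** The qualifier applies, so the patient is naive. The prevalent-user sentence in 7.3.2.1 makes the same patient prevalent.
3. **Either setting, 7.3.2.1.** As a prevalent user, the patient must meet the extra condition. A drug started on day −2 or −1 was not started after diagnosis. The course therefore qualifies only if a different glucocorticoid is started, or dose or schedule changes, after diagnosis. Without that there is no treatment index date (7.2.3). The patient then falls in one of the two groups without glucocorticoid in 7.3.2.3: other treatments only, or no specific treatment.
4. **Time to initiation, 7.7.2.** If the start is accepted, as under the ambulatory naive criterion, the clock that begins at diagnosis gives −2 or −1 days.

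The extra condition also clashes with the window for patients who do have a steroid history. A new drug begun on day −2 or −1 is inside the window but not after diagnosis.

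**Scale.** Section 7.5 gives 153,759 patients in total and around 2,000 in the only hospital database: 2,000 / 153,759 = 1.3%. It gives neither the share treated nor the distribution of start dates, so no count of affected patients follows.

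**The case against.** The strongest reply is that the intent is clear. Three of the four cohort criteria carry the qualifier, so the hospitalized naive line looks like a single omission. The prevalent-user sentence stands under the heading for pre-existing conditions, and the incident-user rule itself opens at day −2, so such patients were presumably meant to be incident. As an account of intent this is fair. It does not settle the text: the hospital criteria as written leave the patient in no cohort, and the requirement that the change come after diagnosis contradicts its own window under any heading. Handling of pre-diagnosis starts in the Kaplan-Meier analysis could be left to the SAP, so the negative times are a consequence to settle, not a separate error.

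A reader might infer more than the protocol supports:

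- **That any prior use makes a patient non-naive everywhere.** The ambulatory naive criterion says otherwise. There the fault is a contradiction between two sections.
- **That the day −2 allowance is void for all prevalent users, or that these patients count as untreated.** A later switch or change of dose or schedule can still qualify them, and some would fall in the group on other treatments only.
- **That the hospital prevalent cohort fills with newly treated patients.** This follows only under the 7.3.2.1 reading. Under 7.2.2.1 they are dropped and that cohort is not inflated. Its size under 7.3.2.1 rests on assumptions. Suppose 40% of 2,000 are treated (800) and 5–20% of them start on day −2 or −1 (40–160). With 40 true prior users the displaced share is 40/80 = 50% to 160/200 = 80%. With 200 it is 40/240 = 17% to 160/360 = 44%. None of these inputs is in the protocol.
- **That these are the sickest patients, treated before a PCR result.** The protocol does not document this. Both hospital cohorts exclude patients with intensive services in the 30 days before or on index, and section 7.9.1 places PCR results in SIDIAP only. In the hospital data the relevant date is therefore a diagnosis code.

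**Conclusion.** The inconsistency stands and should be corrected before the cohorts are built. It follows from the wording alone and is limited to starts on days −2 and −1. On the literal text, a first-ever start on those days has one of two results. In hospital, 7.2.2.1 removes the patient from both cohorts. In either setting, 7.3.2.1 makes the patient prevalent, with a course that does not count on a stable regimen. These are alternative readings and their effects do not add up.

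The number of patients affected is unknown. The cohort loss concerns the single hospital database of around 2,000 patients. In the ambulatory databases the consequence is conflicting labels. The limitations in 7.9.2 cover prior users mislabelled as naive, but not this reverse error.

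**What to change.** - **7.2.2.1 and 7.3.2.1:** use one non-overlapping rule in all four cohort criteria and in the prevalent-user definition. Either end the naive/prevalent look-back at day −3, or apply the exception for COVID-19-related use everywhere. If the exception is used, define unrelated use as use that does not meet the day −2 to day +30 rule, judged on timing and drug list alone so that it does not depend on user type.
- **7.3.2.1, prevalent users:** align the requirement that the new drug or the change come after diagnosis with the stated window, so that it reads on or after day −2.
- **7.7.2:** count starts on day −2 or −1 as initiated at day 0, and report how many there are.

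The cost is a few wording changes and one window in the cohort code. The downside is small: a few unrelated courses that happen to begin on day −2 or −1 will count as COVID-19 starts, which the stated exposure window already accepts.

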7.2.3 Follow-up

Two index date definitions will be applied as appropriate for each objective.

- Diagnosis index date is defined as a positive PCR test for SARS-CoV-2 (labCOVID-19) or a confirmed COVID-19 diagnosis(diagCOVID-19) whichever is the earliest.
- Treatment index date is defined as start of first systemic glucocorticoid treatment episode specifically for the treatment of COVID-19, irrespective of whether the patient is a prevalent or naïve user.

Follow up for all patients will begin from the index date until they experience the outcome of interest (endpoint, depending on the objective) or until cohort exit (date of censoring). The patients will be followed up for maximum 90 days or until censoring occurs, censoring criteria are:

- death
- patient exit (deregister) from a contributing data provider (GP practice)
- end of the database's data collection
- end of study period (latest data cut-off)

The lookback window for evaluating risk factors, medical history is 365 days and will be applied only to outpatient cohorts.

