Steroids often have adjusted dose regimens such that drug may be slowly increased or decreased over time and short acute treatment episodes are also possible. Such changes in dose over time will not be examined, however total cumulative dose will be examined in relation to outcomes of interest (see below).

Cumulative dose

For glucocorticoids used in COVID-19 indication, orally administered, if quantity is available, the formula to calculate the cumulative exposure in mg is described below:

$$Cumulative\ dose_{solid}[mg] = \sum_{all\ exposures} quantity \times amount_value [mg]$$

If the **quantity is missing**, the number of units per day for solid formulations are extracted. The cumulative exposure in mg can then be calculated using the following formula:

$$Cumulative\ dose_{solid}[mg] = \sum_{exposures} units\ per\ day \times amount_value [mg] \times duration$$

For intravenous administration (bolus administration), the dose administered each time will be counted.

$$Cumulative\ dose\ intravenous [mg] = \sum_{all\ exposures} amount_value [mg]$$

Exposure groups for incidence calculation (secondary objective 2 and 3)

For the incidence rates calculation, an on-treatment exposure will be considered with mutually exclusive groups to allow calculation of incidence rates.

Each person will be classified as belonging to one of the following mutually exclusive exposure groups at treatment index date following COVID-19 diagnosis:

- Use of systemic glucocorticoids without other treatments for COVID-19 (drug and respiratory support)
- Use of systemic glucocorticoids plus other treatments for COVID-19 (drug and respiratory support)
- Only other treatments and respiratory support with no systemic glucocorticoids

- No specific treatments for COVID-19 infection (other concomitant treatments for indications other than for COVID-19 are allowed)

A single prescription would be enough to consider the patient as exposed. See section 7.3.2.1 for description of 'other treatment for COVID-19' that are included.

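### For prevalent users still on a course at diagnosis, the rule for a COVID-19 glucocorticoid start ignores the direction of change, so a newly recorded dose reduction counts as an initiation and sets the treatment index date

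*Protocol*

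**What the plan says.** Section 7.3.2.1 explains why a proxy is needed: "As indication is not captured in the available databases". A prevalent user is anyone with at least one exposure to systemic "glucocorticoids in the 120 days prior to diagnosis index date". For such a user, three conditions must hold together before a glucocorticoid counts as started for COVID-19:

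- Timing: "The glucocorticoid treatment was initiated between 2 before and 30 days after COVID-19 diagnosis date".
- Drug: "It is one of the five glucocorticoids recommended for COVID-19 as above".
- Distinction from prior use: either the drug differs from the one used before, or "there is a change in dose or schedule of administration compared to the prevalent use", with the change falling after diagnosis.

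Section 7.2.3 carries this into the analysis: "Treatment index date is defined as start of first systemic glucocorticoid treatment episode specifically for the treatment of COVID-19", for naïve and prevalent users alike. Section 7.3.2.3 starts exposure at the first qualifying record and accepts one prescription as enough. In its text on daily dose, the same section notes: "Steroids often have adjusted dose regimens such that drug may be slowly increased or decreased over time". It then says that these changes over time will not be examined.

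**The concern.** The third condition is meant to separate treatment for COVID-19 from treatment that the patient was already receiving. It asks only whether something changed, so an increase and a reduction are equivalent. A long-term user whose dose is lowered in the month after diagnosis, with a new prescription for the lower dose, meets all the conditions as readily as one whose dose is raised because of COVID-19.

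For the primary objective, this affects the proportion of prevalent users treated, time to initiation and starting dose, and with them duration, cumulative dose and the low/high starting-dose subgroup. For secondary objectives 2 and 3, it affects allocation to the four exposure groups and the date from which follow-up is counted. User type is a reporting stratum throughout, so the error is concentrated in the prevalent-user results and not diluted by naïve users.

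**Working it through.** The protocol gives no figure to reproduce. It has no rate of dose reduction and no rate of COVID-19 treatment among prevalent users. The check is therefore mainly textual.

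**Step 1: does a reduction satisfy the rule?** Take a patient on prednisolone at diagnosis who receives a new prednisolone prescription at a lower dose on day 10.

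- Drug: prednisolone is one of the five. Met.
- Timing: day 10 lies between day −2 and day +30. Met if the new record counts as initiated.
- Distinction: the dose differs from prior use and the change follows diagnosis. Met.

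The only room for doubt is the word initiated. If it excluded every continuing course, the same-drug branch would have almost no content, because it exists to admit changes to a drug already in use. Read together with the first-qualifying-record rule of Section 7.3.2.3, the day-10 prescription qualifies.

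**Step 2: does anything later remove it?**

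- Table 2 measures glucocorticoids for pre-existing conditions only before the diagnosis index date. Continued prior use after diagnosis has no category of its own.
- The prevalent-user sensitivity analysis in Section 7.7.8 excludes patients with short (14-day) prior use. Longer-term users, for whom reductions matter most, remain.
- The limitations in Section 7.9 cover prior users misclassified as naïve, but not this error.

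**Step 3: what would the size depend on?** Let c be the share of prevalent users truly started on a glucocorticoid for COVID-19. Let t be the share of the remainder with a routine dose or schedule change newly recorded in the window. The share of counted starts that are not true starts is

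t(1 − c) / [c + t(1 − c)].

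Both inputs are assumptions; neither is in the protocol.

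| c | t | Calculation | Share |
|---|---|---|---|
| 20% | 5% | 0.040 / 0.240 | 17% |
| 20% | 10% | 0.080 / 0.280 | 29% |
| 10% | 5% | 0.045 / 0.145 | 31% |
| 20% | 30% | 0.240 / 0.440 | 55% |
| 5% | 10% | 0.095 / 0.145 | 66% |
| 5% | 30% | 0.285 / 0.335 | 85% |
| 5% | 40% | 0.380 / 0.430 | 88% |

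Reductions are only part of t, so in each row their own contribution is at most the share shown. Patients with no ongoing course at diagnosis cannot be reducing one, and a single exposure in 120 days is enough to be a prevalent user. That argues against the high values of t. The table shows how strongly the answer depends on unknown inputs; it is not an estimate.

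**The case against.** The strongest case on the other side has five parts.

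1. The conditions are joint and the change is measured against prior use, so a step in a taper already planned could be read as part of the existing schedule. A taper written inside one prescription creates no new record and triggers nothing. This stands in part: a reader might infer that every routine taper becomes a treatment start, and the protocol does not support that. Only newly recorded changes are affected.
2. The sentence on slow increases and decreases sits in the text on dosing of COVID-19 glucocorticoids. It gives no frequency of reductions among chronic users. This stands. The sentence shows awareness that doses change, not how often.
3. A reader might infer that most counted starts are false. Nothing in the protocol fixes c or t, and modest assumptions bring the share down to 17%. This stands.
4. Counting only dose increases or a change of drug looks like the natural remedy, but it would create a new error. A user whose earlier course had ended may truly start the same drug for COVID-19 at an equal or lower dose, and would be recorded as continuing. This stands and shapes the fix.
5. The rule is openly a proxy, comparisons between treatments are out of scope, and an analysis plan could refine the definition. This limits the consequences but does not answer the point. The protocol states the rule in a form that admits reductions, and the distortion is in descriptive quantities that the study exists to report.

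**Conclusion.** The point holds in a limited form. As written, a newly recorded dose reduction in a prevalent user with an ongoing course of a listed drug is counted as a COVID-19 initiation and sets the treatment index date. The proportion of prevalent users counted as treated is biased upward. Time to initiation and starting dose are contaminated by routine prescribing, and some users who only continued prior treatment enter the glucocorticoid groups of objectives 2 and 3.

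The size is unknown. It depends on how many prevalent users have an ongoing course, how often reductions fall in the window, and whether each database creates a new record for them, so it may differ between databases. The conclusion rests on reading initiated so that the same-drug branch keeps its content. The change is worth making before data are analysed, but the material gives no ground for calling the prevalent-user results unusable.

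**What to change.** This is a change to how records are classified, not to any dose or care rule.

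- **Ongoing course of the same drug at diagnosis (current use):** in the main analysis, do not count a recorded reduction as a COVID-19 start. Classify it as continued prior use.
- **Prior course ended (recent or remote use):** count a new course of a listed drug in the window whatever its dose. State this explicitly, because the present wording admits a same-drug restart at the same dose only if the restart is read as a schedule change.
- **Reporting:** tabulate prevalent-user starts by type: different drug, new course after a gap, dose increase, reduction, schedule change only.
- **Sensitivity analysis:** keep the present any-change rule, so nothing is lost.

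Three details need settling at the same time. First, define ongoing: the recency classes in Section 7.3.2.1 leave use that ended 1 to 14 days before diagnosis unassigned. Second, say that the exposure group without systemic glucocorticoids means none for COVID-19, so that continued prior users can be placed. Third, reconcile the window, which opens 2 days before diagnosis, with the third condition, which requires the start or change to follow diagnosis. Section 7.4 lists indication among the prescription fields in LPD Italy and IPCI, despite the statement in Section 7.3.2.1 that it is not captured. If usable, it allows a check of the rule there.

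The cost is moderate. Section 7.3.2.3 derives daily dose only for glucocorticoids deemed to be for COVID-19, so the last pre-diagnosis daily dose must be added for current users. Direction of change may be unreliable where daily dose is imputed under Table 3, and the number of such records should be reported.
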